#### **6.1.5. Medical History and Current Medical Conditions**

Summary (number and percentage) for medical history and current medical conditions will be presented by study treatment sequence for each body system of participants for FAS.

#### **6.1.6. Study Treatment Compliance**

The Cohort 1 and Cohort 2 of the study design is **single** dose 2-sequence, 2-treatment, 4-way cross-over so summary statistics will not be produced for study intervention compliance however listing for dose administration will be created along with exposure data (refer Section 4.5.1).

### **6.2. Appendix 2 Data Derivations Rule**

#### **6.2.1. Criteria for Potential Clinical Importance**

The potential clinical importance (PCI) criteria will not be applicable for the study.

#### **6.2.2. Study Period**

Assessments and events will be classified within each cohort according to the time of occurrence relative to the study treatment period (days).

**Pre-Treatment:** For the presentation of serious adverse events (SAEs), concomitant medications, and other assessments in pre-treatment is defined as -

Date of assessment < Study treatment start date of period 1 (day 1).

**On-Treatment:** For the presentation of adverse events (AEs), serious adverse events (SAEs), concomitant medications, 12-lead ECG, vital signs, and other assessments in on-treatment is defined as -

Study treatment start date of period 1 (day 1) <= Date of assessment <= Study treatment stop date of period 4 (Day 10) or early withdrawal + 1 day

Worsening in AE (change in AE severity from lower severity to higher severity category) relative to the pre-study treatment state will also be considered as on-treatment AE.

If time of assessment or study treatment is not collected (missed), the following assessment on the first dose date will be assumed to be taken prior to the first dose and therefore considered pre-treatment.

As per study design, Four Treatment Periods of the study are defined below.

#### **Treatment Period 1 (Day1):**

Treatment Period 1 dose start time <= Treatment Period 1 < Treatment Period 2 dose start time

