- j. **MDI training:** Participants will be trained using a placebo HFA-134a propellant via an MDI on Day-1 and prior to dosing on each dosing day (Day 1, 4, 7 and 10). On dosing days, participants should review the instructions use the placebo MDI. The investigator or delegate are to observe the participant performing a single puff using the placebo MDI and provide feedback as necessary until proper technique is observed before conducting the full dose using the investigational inhaler. Additional training using the placebo MDI (e.g., on Day 3) may be performed at the discretion of the site.
- k. **Administration of study intervention:** 8 inhalations of 100 µg (800 µg total) of study intervention or 2 inhalations of 100 µg (200 µg total) of study intervention, with the inhalations administered at 20-second intervals.
- l. **PK blood sampling:** on each dosing day (Day 1, 4, 7 and 10) PK blood samples will be taken at predose, at 3, 5, 10, 15-, 20-, 30-, and 45-minutes postdose; and at 1, 1.5, 2, 3, 4, 5, 6, 8, 10-, 12-, 16- and 24-hours postdose for plasma salbutamol determination. PK collection will be from the start of study intervention (first inhalation).
- m. **AE and SAE review:** AEs will be collected from the start of study intervention until final follow-up telephone call. SAEs will be collected from the signing of the ICF until final follow-up telephone call.

Table 2 Timing of Assessments

Assessment	Timing of Dosing
Study intervention administration	Dosing for each participant will be around the same time (± 1 hour) at each intervention period day. All postdose timepoints will be from the start of each study intervention i.e., the first inhalation.
PK blood sampling	Predose samples will be obtained between waking up and dosing. Postdose samples up to 30 minutes will be obtained with a time window of ± 1 minute. Thereafter, postdose samples will be obtained with time margins of $\pm 5\%$ of the time that has passed since (last) dosing.
PD blood sampling	For PD blood samples, predose samples will be obtained between waking up and dosing. Postdose samples up to 30 minutes will be obtained with a time window of ± 2 minutes. Thereafter, postdose samples will be obtained with time margins of $\pm 5\%$ of the time that has passed since (last) dosing.

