3.2.3. Estimands supporting secondary safety objectives

Cohort 1:

Test: Salbutamol HFA-152a MDI 200 µg

Reference: Salbutamol HFA-134a MDI 200 µg

The clinical question of interest for the safety secondary objective in Cohort 1 is –

What is the safety and tolerability profile of single doses 200 µg of salbutamol in Cohort 1 healthy participants delivered via MDIs?

The secondary safety estimand for Cohort 1 is described by the following attributes:

- The population is healthy male or female participants aged 18 to 55 years.
- The secondary safety endpoints are:
 - Incidence of AEs and SAEs
 - Absolute values for predose and postdose 12-lead ECGs recording of HR and QTc intervals at each assessed visit
 - Change from baseline for postdose 12-lead ECGs recording of HR and QTc intervals at each assessed visit
 - Absolute values of clinical laboratory parameters at each assessed visit
 - Absolute values of vital signs (systolic and diastolic blood pressure and pulse rate) at each assessed visit.
- Treatment condition is administration of salbutamol as a single 200 µg dose, given as 2 actuations each separated by a 20-second interval, each delivering 100 µg of salbutamol (as salbutamol sulfate) as the ex-valve dose for the HFA-152a MDI or HFA-134a MDI.
- The ICEs and estimand strategies are as follows:
 - Study treatment discontinuation due to any reason (treatment policy strategy). Interest lies in the group of participants irrespective of whether they completed the study intervention.
 - Occurrence of emesis or coughing on dosing (treatment policy strategy).
 - Dosing error: Considered less than or more than prescribed dose (treatment policy strategy).
 - Use of prohibited or rescue medication which is impacted to PK parameters (Treatment policy strategy).
- The population-level summary to be estimated are:
 - Number and percentages for incidence of AEs and SAEs
 - Mean of absolute values for 12-lead ECGs recording of HR and QTc intervals at each assessed visit
 - Mean of change from baseline values for postdose 12-lead ECGs recording of HR and QTc intervals at each assessed visit
 - Mean of absolute of clinical laboratory parameters including vital signs (systolic and diastolic blood pressure and pulse rate) at each assessed visit

Cohort 2:

Test: Salbutamol HFA-152a MDI 800 µg

Reference: Salbutamol HFA-134a MDI 800 µg

The clinical question of interest for the safety secondary objective in Cohort 2 is –

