**Table 1 Baseline Definition for Laboratory PD and Safety Parameters and Safety Endpoints**

	Baseline To be used in Analysis/Summaries			
	Period 1	Period 2	Period 3	Period 4
Laboratory PD and Safety parameters - Serum potassium (PD) and Glucose (safety) Safety endpoints - 12-lead ECG [1][2] Vital Signs	Predose Day 1	Predose Day 4	Predose Day 7	Predose Day 10

[1] Taken in triplicate.

[2] Mean of the triplicate 12-lead ECG measurement from the Day 1 assessment (pre-dose).

For safety endpoints, if a pre-dose observation of day i (where i = 1,4,7 and 10) is missing in a given period, then the day-1 or screening (latest available observation) value may be used as baseline.

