#### **Treatment Period 2 (Day4):**

Treatment Period 2 dose start time <= Treatment Period 2 < Treatment Period 3 dose start time

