#### **Treatment Period 3 (Day7):**

Treatment Period 3 dose start time <= Treatment Period 3 < Treatment Period 4 dose start time

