#### **Treatment Period 4 (Day10):**

Treatment Period 4 dose start time <= Treatment Period 4 < Treatment Period 4 dose start time +1 day

**Post-Treatment:** For the presentation of adverse events (AEs), serious adverse events (SAEs), concomitant medications, 12-lead ECG, vital signs and laboratory assessments in post-treatment is defined as

Date of assessment > Study treatment stop date of period 4 (Day 10) or early withdrawal + 1 day.

Please refer Section [6.2.6](#) for handling of missing and partial dates of assessments.

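### SAP 6.2.2 opens each treatment period at dose start, so the Day 4, 7 and 10 predose safety readings fall in the previous period, in conflict with SAP Table 1 (minor)

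*SAP*

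**What the plan says.** SAP 6.2.2 (Study Period) sets the scope of its rule: "Assessments and events will be classified within each cohort according to the time of occurrence relative to the study treatment period (days". Its on-treatment paragraph names ECG and vital signs, so the section is not confined to adverse events. The four windows are:

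- Period 1: "Treatment Period 1 dose start time <= Treatment Period 1 < Treatment Period 2 dose start time"
- Period 2: "Treatment Period 2 dose start time <= Treatment Period 2 < Treatment Period 3 dose start time"
- Period 3: "Treatment Period 3 dose start time <= Treatment Period 3 < Treatment Period 4 dose start time"
- Period 4: "Treatment Period 4 dose start time <= Treatment Period 4 < Treatment Period 4 dose start time +1 day"

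SAP 4.1.2, Table 1, takes the predose readings of Days 1, 4, 7 and 10 as the baselines of Periods 1, 2, 3 and 4. It covers serum potassium, glucose, 12-lead ECG and vital signs. Its missing-data note speaks of what happens "if a pre-dose observation of day i (where i = 1,4,7 and 10) is missing in a given period", so it treats a predose reading as part of the period about to be dosed.

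On timing, Protocol 1.3 (Table 2) has predose safety and PD readings taken after the participant wakes and before the dose. It also says: "All postdose timepoints will be from the start of each study intervention i.e., the first inhalation".

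On use, Protocol 3.2.3 lists as a secondary safety endpoint "Absolute values for predose and postdose 12-lead ECGs recording of HR and QTc intervals at each assessed visit". SAP 4.5 summarises safety data by study treatment. SAP 4.5.3.1 and 4.5.3.2 call for laboratory and vital-sign listings by treatment and period, and SAP 4.5.3.3 for ECG listings by sequence and period.

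**The concern.** Two SAP rules give the same reading different periods. Section 6.2.2 has no exception for predose readings and does not refer to Table 1. Table 1 settles which value is the baseline, but not which period or product label the reading carries elsewhere.

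In a crossover the period determines the product. A programmer who derives the period variable from 6.2.2 and reads treatment from it would tabulate some predose values under the product given three days earlier. The outputs at risk are the absolute-value safety summaries by treatment and the listings by period. The exploratory PD extremes (minimum potassium, maximum heart rate, maximum QTc) are at risk only if they are taken over every reading in a period window. The Period 4 window has a separate gap at 24 h.

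**Working it through.** The plan states no figure to reproduce; the check is a classification.

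**Inputs.** Doses on Days 1, 4, 7 and 10 (Protocol 4.1), taken as 0, 72, 144 and 216 h. Sequences TRRT and RTTR, with 15 participants each per cohort (Protocol 4.1). Dose start is taken as the first inhalation, which is the protocol's timing convention; SAP 6.2.2 says only dose start time. A predose reading is placed at dose time minus x; x from 1 minute to 3 hours was tried, and any x > 0 within that range gives the same result.

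**Windows under 6.2.2.** Period 1 = [0, 72), Period 2 = [72, 144), Period 3 = [144, 216), Period 4 = [216, 240) h.

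**Placement.**

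| Predose reading | Period by 6.2.2 | Period by Table 1 | TRRT product: 6.2.2 / Table 1 | RTTR product: 6.2.2 / Table 1 |
|---|---|---|---|---|
| Day 1 | none | 1 | none / T | none / R |
| Day 4 | 1 | 2 | T / R | R / T |
| Day 7 | 2 | 3 | R / R | T / T |
| Day 10 | 3 | 4 | R / T | T / R |

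**Counts.** Call one participant's ECG, vital-sign and potassium/glucose readings before one dose a predose set. If all 30 participants in a cohort complete:

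- sets in total: 4 × 30 = 120
- assigned to an earlier period than in Table 1 (Days 4, 7, 10): 3 × 30 = 90
- labelled with the other product (Days 4, 10): 2 × 30 = 60, that is 60/120 = 50%

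The swaps balance. On Day 4, 15 R sets go to T (TRRT) and 15 T sets go to R (RTTR). On Day 10, 15 T sets go to R (TRRT) and 15 R sets go to T (RTTR). That makes 30 in each direction.

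**Period 4.** The window ends strictly before 216 + 24 = 240 h. A reading at 23.99 h is inside; one at exactly 24 h or later is in no period. The protocol margin for the 24-h PK sample is 5% of 24 h = 1.2 h, so a valid sample may be drawn from 22.8 to 25.2 h, and those from 24 to 25.2 h fall outside. The general On-Treatment rule works by date and runs to Day 10 + 1 = Day 11, so it does include them.

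**PD extremes.** SAP 4.4 gives no window for them. The protocol schedules one postdose ECG per dosing day, at 30 minutes (Protocol 1.3, note i). If a maximum were taken over the whole 6.2.2 window, Periods 1 to 3 would add the next dose's predose triplicate to that reading, and Period 4 would have no such addition. The documents give neither that rule nor a variance, so no size can be attached.

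**The case against.** The strongest reply is that a sensible programmer would treat scheduled assessments nominally. SAP 6.2.4 adopts the protocol's assessment windows for the analysis. SAP 4.5.3.3 specifies ECG summaries by predose and postdose on each dosing day. Table 1 is a specific rule for baselines, and a general window does not displace it. The 6.2.2 windows also match the adverse-event attribution rule in SAP 4.5.2, which suggests they were written with events in mind.

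Much of this stands. It makes the nominal reading likely, and it means the 60 sets are labels at risk under a literal reading, not values known to be misreported. The protocol also expects the washout of at least 72 h to remove carryover (Protocol 4.2). If so, predose values carry little product effect under either label, and the swaps balance between products.

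It does not remove the conflict. Section 6.2.2 says in terms that it covers assessments, and none of these sections says which rule prevails for absolute values by treatment or for listings by period.

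**Conclusion.** The point holds as a minor defect: 6.2.2 is wrong as written for scheduled assessments. Up to 60 of 120 predose sets per cohort carry the wrong product label if it is followed literally. That count assumes 30 completers and that product is read from the 6.2.2 period.

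Four stronger conclusions that a reader might draw are not supported:

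- *Baselines are lost or wrong.* Table 1 fixes the baseline for each period, and the change-from-baseline definition after Table 2 uses it at each dosing period.
- *Predose PK samples contradict Table 1.* Table 1 does not list PK. Protocol 1.3, note l, ties the predose PK sample to its own dosing day, and PK parameters come from noncompartmental analysis on actual sampling times (Protocol 9.3.1). Nothing shows that the 6.2.2 windows select PK samples, so neither the predose rule nor the 24-h gap is shown to affect a PK parameter.
- *Day 1 predose readings are Pre-Treatment.* That category requires a date before the first dosing date. Day 1 predose shares that date and is On-Treatment, although in no numbered period. The pre-treatment fallback applies only when a time is missing.
- *The test/reference comparison of maximum QTcF is diluted.* This needs a derivation over the whole period window, which no section states. The SAP version history describes a single PD observation per participant for the study, and the documents give no standard deviation or correlation. These endpoints are exploratory.

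**What to change.** Amend SAP 6.2.2 as follows:

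1. Assign scheduled assessments by nominal day and time point. Predose assessments on Days 1, 4, 7 and 10 belong to the period dosed that day, as in Table 1.
2. Keep the dose-start-to-dose-start windows for adverse events, consistent with SAP 4.5.2.
3. Let Period 4 include the nominal 24-h assessments, whether taken on time or within the allowed margin.

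In SAP 4.4, state that minimum potassium, maximum heart rate and maximum QTcF use postdose readings of the same dosing day only.

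The cost is a few sentences in the SAP and the matching lines of the programming specification. No new data are needed, and the design and sample size are unaffected.

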#### **Treatment Period 2 (Day4):**

Treatment Period 2 dose start time <= Treatment Period 2 < Treatment Period 3 dose start time

#### **Treatment Period 3 (Day7):**

Treatment Period 3 dose start time <= Treatment Period 3 < Treatment Period 4 dose start time

#### **Treatment Period 4 (Day10):**

Treatment Period 4 dose start time <= Treatment Period 4 < Treatment Period 4 dose start time +1 day

**Post-Treatment:** For the presentation of adverse events (AEs), serious adverse events (SAEs), concomitant medications, 12-lead ECG, vital signs and laboratory assessments in post-treatment is defined as

Date of assessment > Study treatment stop date of period 4 (Day 10) or early withdrawal + 1 day.

Please refer Section [6.2.6](#) for handling of missing and partial dates of assessments.

#### **6.2.3. Study Day and Reference Dates**

CCI

CCI

#### **6.2.4. Assessment Window**

Protocol assessment window as defined in protocol Section 1.3 will be followed for the statistical analysis.

#### **6.2.5. Multiple measurements at One Analysis Time Point**

When triplicate 12-lead ECG assessments are taken, the mean of the 3 measurements will be calculated first and summary statistics will be based on the calculated mean.

If multiple assessments are taken from the same type for lab parameter or other assessments, the worst case will be used.

[figure not shown]
#### **6.2.6. Handling of Partial Dates**

CCI

[figure not shown]
**CONFIDENTIAL**

219728

CCI

CCI

### **6.2.7. Trademarks**

Trademarks of the GlaxoSmithKline Group of Companies
METEOR

Trademarks not owned by the GlaxoSmithKline Group of Companies
MedDRA
SAS
WinNonlin

### 6.3. Appendix 3 List of Abbreviations and Definitions of Terms

Abbreviation	Definition
AE	Adverse event
AESI	Adverse event of special interest
ALT	Alanine transaminase
AM	Arithmetic mean
AST	Aspartate aminotransferase
AUC (0-∞)	Area under the curve (from zero to infinity)
AUC(0-last)	Area under the curve (from zero to last)
BMI	Body mass index
CI	Confidence intervals
Cmax	Maximum plasma concentration
COVID-19	Coronavirus disease 2019
CPK	Creatine phosphokinase
CRF	Case report form
CSR	Clinical study report
CVb	Between subject coefficient of variation
CVw	Within subject coefficient of variation
ECG	Electrocardiogram
eCRF	Electronic case report form
eGFR	Estimated Glomerular Filtration Rate
EMA	European Medicines Agency
FAS	Full analysis set
FDA	Food and Drug Administration, United States of America

Abbreviation	Definition
FSFV	First subject first visit
GCP	Good Clinical Practice
GM	Geometric mean
GMR	Geometric mean ratio
HBsAg	Hepatitis B surface antigen
HFA	Hydrofluoroalkane
HFA-134a	1,1,1,2-tetrafluoroethane
HFA-152a	1,1-difluoroethane
HIV	Human immunodeficiency virus
HR	Heart rate
ICE	Intercurrent event
ICF	Informed consent form
ICH	International Council for Harmonisation
IDSL	Integrated Data Standards Library
LLOQ	Lower Limit of Quantification
LSLV	Last Subject Last Visit
MDI	Metered Dose Inhaler
MedDRA	Medical Dictionary for Regulatory Activities
MHR	Maximum Heart Rate
PD	Pharmacodynamic(s)
PK	Pharmacokinetic(s)
PR	Pulse Rate
QTc	Corrected QT interval

Abbreviation	Definition
QTcF	QT interval corrected using Fridericia's formula
RR	Respiratory Rate
RSABE	Reference-scaled average bioequivalence
SADE	Serious adverse device effect
SAE	Serious adverse event
SD	Standard Deviation
SE	Standard Error
SmPC	Summary of product characteristics
SoA	Schedule of activities
TEAE	Treatment-emergent adverse event
Tmax	Time to reach maximum plasma concentration
ULN	Upper limit of normal
WHO	World Health Organization

[figure not shown]
#### 6.4. Appendix 4 Standard Error (SE) Calculation for 2x2x4 Full Replicate Design

CCI

**CONFIDENTIAL**

219728

[figure not shown]
CCI

**CONFIDENTIAL**

219728

[figure not shown]
CCI

**CONFIDENTIAL**

219728

CCI

**CONFIDENTIAL**

219728

[figure not shown]
CCI

**CONFIDENTIAL**

219728

[figure not shown]
CCI

**CONFIDENTIAL**

219728

CCI

CCI

## 6.6. Appendix 5 Maintaining Integrity of Accumulating Data

**Table 10      Maintaining Integrity of Accumulating Data in the Randomized Open-Label Double-Arm Study**

Objective/ deliverable	Milestone	Responsible	Outputs Reviewer's
Dry run	Dry run will be performed as per GSK SOP		Clinical Development Lead Clinical Science Lead Medical Monitor CPMS Team Medical Writer Team SERM Team Regulatory Team “Safety team and Medical Monitor will review aggregate safety data and individual cases prior to SRT. Summary and safety conclusion and benefit/risk will be presented at SRT”. Statistical and Programming team.
Interim Analysis (IA) SAC	Once Cohort 1 participants completed the study	Statistical and Programming team	Outputs of SAC will be shared by S&P team with cross functional team
Final Analysis SAC	2 weeks after the DBL of study		

Study data will be shared with only core study team members for their review during the study trial phase as mentioned in outputs reviewer's column of the [Table 10](#).

